The dysregulation of the Wnt/β-catenin signaling pathway is closely linked to the development and progression of various cancers, particularly in colorectal cancer (CRC) [12]. The YWHA (14-3-3) family of proteins is widely expressed in eukaryotic cells, including seven subtypes: 14-3-3 β (YWHAB), 14-3-3 γ (YWHAG), 14-3-3 ϵ (YWAH), 14-3-3 ζ (YWAZ), 14-3-3 σ (YWHAS) and 14-3-3 τ/θ (YWAQ)[13].. These 14-3-3 isoforms exhibit highly conserved structures across different species and can form both homodimers and heterodimers, acting as molecular connectors through protein-protein interactions [14]. As the central hub of various signaling pathways, 14-3-3 proteins are involved in numerous cellular processes, including cell cycle regulation, protein transport, apoptosis, and neuronal plasticity [13-15]. More importantly, dysregulation of 14-3-3 proteins is associated with multiple diseases, such as cancer, autoimmune disorders, and metabolic disorders [13,16]. Our preliminary research has identified that the amplification of YWHAB (14-3-3 β) is a key

driver of copy number variations (CNVs) in cancer cells and is associated with poor outcomes in CRC patients, suggesting its potential as a biomarker for prognosis. Furthermore, experimental evidence from cell studies and mouse models indicates that YWHAB enhances glycolysis and nucleotide metabolism, thereby promoting chemotherapy resistance in colorectal cancer (CRC). Mechanistically, YWHAB interacts with β -TrCP and competitively binds to β -catenin, inhibiting the degradation of β -catenin mediated by β -TrCP, thus promoting the development and progression of CRC and its chemotherapy resistance. Additionally, through large-scale molecular docking and drug binding affinity screening, we discovered that FDA-approved drugs hesperidin and diosmin can specifically block the interaction between YWHAB and β -TrCP, significantly enhancing the sensitivity of YWHAB high-expressing CRC organoids and patient-derived xenografts (PDX) to FOLFOX treatment. Therefore, our research has provided a deeper understanding of the chemotherapy resistance mechanism in YWHAB high-expressing CRC. The expression level of YWHAB can serve as a potential biomarker for predicting chemotherapy sensitivity in CRC patients and for achieving precise chemotherapy. Blocking the YWHAB/ β -TrCP/ β -catenin signaling axis is expected to be an important approach to improve the chemotherapy sensitivity of YWHAB high-expressing CRC patients.

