therapeutic potential[20-22]. Clinical trials and practices have confirmed the therapeutic effects of naringin and dasiglucoside on various diseases, including cardiovascular disease, neurological disorders, type 2 diabetes, venous ulcers, hemorrhoids, fatty liver disease associated with metabolic dysfunction, and cancer[23]. Previous studies [23] have found that naringin can inhibit the protein expression level of nitric oxide synthase (iNOS), thereby reducing the production of nitrogen dioxide and prostaglandin E2 (PGE2); therefore, naringin is considered an inhibitor of cyclooxygenase-2 and iNOS, which may explain its anti-tumor and anti-inflammatory properties. A study in 2022 found that naringin has chemopreventive potential in colorectal cancer (CRC) induced by 1,2-dimethylhydrazine (DMH), and naringin prevents CRC in vivo by regulating the Smad4 and activin A signaling pathways[24]. Another study reported that hesperidin can effectively prevent the incidence of intestinal tumors in mice induced by azoxymethane [25]. In our preliminary research, we discovered through microscale thermophoresis (MST) experiments that hesperidin has a strong binding affinity with YWHAB protein. Both in vitro and in vivo experiments have shown that hesperidin and docetaxel can effectively inhibit the interaction between YWHAB and β -TrCP. Animal experiments further suggest that, compared to the FOLFOX regimen alone, combining citrus flavonoid tablets (Aimalang, each tablet containing 500mg of citrus flavonoids, 90% docetaxel, and 10% hesperidin) with the FOLFOX regimen can enhance the inhibitory effect of FOLFOX on PDX tumors. These in vitro and in vivo results fully confirm that the combination of FOLFOX and citrus flavonoid tablets (Aimalang) can serve as a potential treatment option for patients with high YWHAB expression CRC, although this needs to be further confirmed through prospective clinical trials.

Although the efficacy of citrus flavonoid tablets in treating various diseases has been confirmed through extensive clinical research and practice, most clinical trials use 300-600 mg of pure hesperidin for oral supplementation. However, due to its extremely low water solubility, hesperidin has a relatively low bioavailability [21,26,27]. After comprehensive consideration, we plan to use

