citrus flavonoid tablets (Aimalang) as an alternative to citrus flavonoids in our clinical trials. In clinical practice, citrus flavonoid tablets (Aimalang) are commonly used to treat various symptoms associated with venous and lymphatic insufficiency, as well as acute hemorrhoids. Our preliminary studies have shown that docetaxel, hesperidin, and citrus flavonoid tablets (Aimalang) can effectively inhibit the interaction between YWHAB and β -TrCP, thereby enhancing the anti-tumor effects of FOLFOX. Furthermore, Aimalang has been clinically applied, and its safety has been confirmed. Therefore, based on our preliminary research and safety findings, using Aimalang as an alternative to hesperidin to explore the neoadjuvant treatment effects of FOLFOX combined with Aimalang in locally advanced rectal cancer with high YWHAB expression is both safe and reasonable.

A common strategy to improve tumor regression in patients with locally advanced rectal cancer is to enhance neoadjuvant therapy by adding systemic chemotherapy before radiotherapy and chemotherapy. Several Phase II clinical trials have shown that [28-31] systemic adjuvant chemotherapy before radiotherapy and chemotherapy can enhance the anti-tumor response in patients with large primary tumors near the mesorectal fascia. In these trials, the proportion of patients achieving pathological complete remission slightly improved after systemic adjuvant chemotherapy before radiotherapy and chemotherapy. In 2004, a German clinical trial named CAO/ARO/AIO-94 established preoperative infusion of fluorouracil as the standard combination therapy for locally advanced rectal cancer [32]. In 2015, the CAO/ARO/AIO-04 trial [33] added oxaliplatin to neoadjuvant radiotherapy and chemotherapy based on fluorouracil, significantly improving the disease-free survival rate in patients with cT3-4 or cN1-2 locally advanced rectal cancer. The protocol established by CAO/ARO/AIO-04 is also considered a new treatment option for patients with locally advanced rectal cancer. Our center has conducted a series of prospective studies in the field of adjuvant/neoadjuvant chemotherapy for locally advanced rectal cancer, such as the FOWARC study, and the relevant research findings have

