4.1 Study treatment grouping

This study is a prospective, open-label, double-arm, Phase II clinical trial that includes a neoadjuvant treatment group using the mFOLFOX6 regimen and a neoadjuvant treatment group combining the mFOLFOX6 regimen with Citrus Flavonoid Tablets (Aimalang). The study aims to enroll patients with locally advanced rectal cancer who are in clinical stage I, II, or III. Endoscopic biopsy specimens will be collected for YWHAB immunohistochemical testing to identify patients with high YWHAB expression in locally advanced rectal cancer. These patients will then be randomly assigned to either the mFOLFOX6 treatment group or the mFOLFOX6 combined with Citrus Flavonoid Tablets (Aimalang) treatment group for neoadjuvant therapy. The mFOLFOX6 regimen involves 4-6 cycles before surgery and 6-8 cycles after surgery, with each cycle lasting 14 days: on day 1, 85 mg/m² of oxaliplatin is administered intravenously over 180 minutes; on day 1, 400 mg/m² of leucovorin is administered intravenously over 120 minutes; and on day 1, 2400 mg/m² of 5-fluorouracil is administered continuously intravenously for 46 hours. The Citrus Flavonoid Tablets (Aimalang) treatment regimen involves taking 500mg of Citrus Flavonoid Tablets (Aimalang) orally three times daily, with doses given on days 1-14 of each 14-day cycle.

This trial allows for dose adjustments. Patients who experience disease progression during neoadjuvant therapy may stop the study treatment and directly undergo surgery or follow local guidelines. If a patient cannot tolerate the planned 6 cycles of neoadjuvant therapy, early surgery can be considered. Any patient who has received another anticancer regimen before surgery will stop the study treatment and be managed according to local guidelines. The postoperative

treatment for both groups is determined by the investigator, which may include continuing the mFOLFOX6 regimen combined with Citrus Flavonoid Tablets (Aimalang). It is important to note that all patients in the control group are prohibited from taking Citrus Flavonoid Tablets (Aimalang) without authorization during the trial. If a patient needs to take this medication for any reason, they should consult their primary physician, who will decide whether to use an alternative or discontinue the patient's participation in the trial.

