4.3 Combination and concomitant drugs

4.3.1 Prohibited combination and concomitant drugs

No other anti-tumor treatment is allowed during the study, including: chemotherapy, molecular targeted therapy, hormone therapy, immunotherapy, biological therapy, non-palliative radiotherapy and immunomodulators (including but not limited to: interferon, interleukin-2, etc.).

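### The control-arm ban is written around the tablet rather than its active ingredients, and no visit list requires other hesperidin or diosmin products to be recorded

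*Combined protocol and SAP*

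**What the plan says.** Protocol section 4.1 tries to prevent contamination. It says that "all patients in the control group are prohibited from taking Citrus Flavonoid Tablets (Aimalang) without authorization during the trial". It continues: "If a patient needs to take this medication for any reason, they should consult their primary physician". That doctor is the person "who will decide whether to use an alternative or discontinue"; discontinuing here means leaving the trial. The alternative is not defined further.

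Section 4.3.1 begins "No other anti-tumor treatment is allowed during the study", and 4.3.2 keeps to the same subject. Neither mentions flavonoid, hesperidin or diosmin products, and nor do the exclusion criteria in 3.2.

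The Background (section 1) puts the rationale at ingredient level: "FDA-approved drugs hesperidin and diosmin can specifically block the interaction between YWHAB" and β-TrCP. It notes that "most clinical trials use 300-600 mg of pure hesperidin for oral supplementation", and that "due to its extremely low water solubility, hesperidin has a relatively low bioavailability". It gives the tablet's usual uses as symptoms of venous and lymphatic insufficiency, "as well as acute hemorrhoids". Criterion 3.1(1), as written, requires that colonoscopy or physical examination point to haemorrhoids.

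On recording, screening (5.1) lists cancer treatment history. The lists in 5.2 and 5.3 cover examinations, laboratory tests, ECG and adverse events, with imaging as well in 5.2. None has a concomitant-medication item. Follow-up (5.4) collects later anti-tumour treatment only.

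**The concern.** The main objective (2.2) is to show that adding the tablet raises the ypTNM 0-I rate. The contrast is clean only if controls do not receive the same active agents before the surgical specimen is taken. That window is 4-6 cycles of 14 days, or 8-12 weeks.

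A ban on the product does not fully protect a contrast whose rationale is the ingredient. A control who takes a separate hesperidin or diosmin product has not clearly broken 4.1 or 4.3. The withdrawal rule in 3.3(5) and the per-protocol definition in 8.1 both act on significant deviations, so they would not clearly apply. Without a required medication record, such use might also go unseen.

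If the ingredients work as hypothesised, exposed controls do better and the observed difference shrinks. A real effect could be missed. A false positive would not be created this way.

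**Working it through.** **1. Scope of the rules.**

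- Ban (4.1): the citrus flavonoid tablet, with the brand in brackets. Read generically, it may reach other citrus flavonoid tablets. Separate hesperidin or diosmin medicines and supplements are not clearly covered.
- Prohibited drugs (4.3.1-4.3.2): anti-tumour treatment only.
- Active agents (Background): hesperidin and diosmin. The tablet's composition names hesperidin directly. The 90% component is printed as docetaxel, so diosmin as a tablet ingredient is inferred from the rationale. The point stands on hesperidin alone.
- Recording (5.1-5.3): no concomitant-medication item.

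**2. The plan's own figure.** Section 8.5 gives 25% versus 40%, significance level 0.05 (sidedness not stated), power 0.8, 10% dropout and 236 patients. With a one-sided test and unpooled variance, n per arm = (1.645 + 0.842)² × (0.25×0.75 + 0.40×0.60) / 0.15² = 117.5, rounded up to 118, so 236 in total. This match contains no dropout allowance; with 10% dropout the same formula gives 264. That mismatch is a separate matter. Here it only explains why the base case is one-sided with 118 per arm.

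**3. Illustration of dilution.** Let c be the share of controls exposed and e the share of the effect they obtain. The documents give neither; c = 0-20% and e = 1 or 0.5 are assumptions.

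- Control rate: p_C = 0.25 + 0.15 × c × e. Experimental rate: p_E = 0.40.
- Power = Φ{[(p_E − p_C) − z·√(2p̄(1−p̄)/n)] / √([p_C(1−p_C) + p_E(1−p_E)]/n)}, where p̄ is the mean of the two rates. Section 8.3 names no test for this comparison, so the pooled z test is assumed, as is 1:1 allocation.
- Example, c = 0, n = 118, one-sided: (0.15 − 1.645×0.0610)/0.0602 = 0.826, power 79.6%.
- Example, c = 0.10, e = 1: p_C = 0.265; (0.135 − 1.645×0.0613)/0.0607 = 0.562, power 71.3%.

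Power (%) by share of controls exposed:

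| Setting | 0% | 2% | 5% | 10% | 20% |
|---|---|---|---|---|---|
| One-sided, 118 per arm, full effect | 79.6 | 78.0 | 75.6 | 71.3 | 61.9 |
| One-sided, 118 per arm, half effect | 79.6 | 78.8 | 77.6 | 75.6 | 71.3 |
| One-sided, 106 per arm (118 × 0.9), full effect | 75.7 | 74.1 | 71.6 | 67.2 | 58.0 |
| One-sided, 106 per arm, half effect | 75.7 | 74.9 | 73.7 | 71.6 | 67.2 |
| Two-sided, 118 per arm, full effect | 69.4 | 67.5 | 64.6 | 59.6 | 49.4 |
| Two-sided, 118 per arm, half effect | 69.4 | 68.4 | 67.0 | 64.6 | 59.6 |

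In the base case the loss is about 1-4 points at 2-5% exposed and 4-8 points at 10%. The full-effect rows are best read as upper bounds. They imply exposure equal to 500 mg three times daily throughout neoadjuvant treatment, and the Background itself describes hesperidin as poorly bioavailable.

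**The case against.** **Purpose of 4.1.** A reader might infer that 4.1 invites a physician to give a control the same ingredients as the alternative. The wording does not forbid it, but the clause is plainly meant to keep controls off the study agent, and discontinuation as the other option makes sense only on that reading. A same-ingredient alternative is unlikely. What stands is that separate products are not clearly barred.

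**Uneven translation.** The product's name varies across the protocol and one ingredient appears to be mistranslated, so fine wording is weak evidence. This is fair, and it limits the weight of the point. It does not supply the missing rule on ingredients.

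**Traceability.** A reader might infer that the trial could not know about control exposure at all. The documents do not support that. Section 7.2 counts worsening of an existing condition as an adverse event, 5.2 has adverse events documented before each administration, and 7.6.1 has investigators ask about them at each follow-up visit. Causality assessment (7.5.2) considers concomitant treatments, 7.5.3 refers to changes in concomitant therapy, and section 10 provides source verification. A treated haemorrhoid flare could well be traced. The CRF is not supplied and may have a medication page. What stands is that this is partial: it follows events rather than medication, and it would not reliably catch self-bought products.

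**No evidence of exposure.** Signs of haemorrhoids do not imply treatment, use for acute haemorrhoids need not be sustained, and the remark on pure hesperidin describes dosing in trials rather than patients' own habits. All of this stands, and it is why the power table is illustration only.

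**Conclusion.** The point holds as a minor one, with medium confidence. The rule that protects the primary contrast is set by product, while the rationale is set by ingredient. Controls could therefore take the agents under test without a clear deviation and without a required record. The haemorrhoid criterion makes some exposure before surgery plausible.

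The documents do not show that contamination will occur or how often, so no particular loss of power can be claimed. The direction of any bias, toward no difference, rests on the assumption that the ingredients help. The figures also rest on 1:1 allocation, a pooled z test and, in the base case, a one-sided 0.05 level. Nothing here threatens the trial's validity in the sense of a false positive, and ITT remains the right main efficacy set.

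**What to change.** - **4.1 and 4.3.1:** from randomisation to surgery, prohibit medicines and supplements containing hesperidin or diosmin in the control arm, and any beyond the assigned tablet in the experimental arm. Exempt ordinary food explicitly, since these are citrus compounds and a literal ban would reach fruit and juice.
- **4.1:** state that the alternative must contain neither ingredient. The choice among other haemorrhoid treatments stays with the physician.
- **5.1 and 5.2:** add a concomitant-medication item (product, dose, dates) at screening and each cycle visit, if the CRF does not already have one.
- **8.1:** keep ITT primary. Count such use as a per-protocol deviation only above a dose or duration threshold fixed in advance and judged before outcome data are seen. This keeps to the existing limit in 8.1, that a deviation must bear on the efficacy assessment, and avoids dropping controls for trivial use.

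The cost is a few sentences and at most one more CRF item. The downside is slightly fewer haemorrhoid products open to controls before surgery.

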4.2 Dose adjustment of the investigational drug

4.2.1 Protocol for discontinuation or dose adjustment of treatment

During the study treatment, adverse events will be continuously monitored, and participants will be instructed to promptly inform their attending physician of any adverse events. In cases of mild toxicity, if the investigator, after consultation with the medical monitor or sponsor, deems that dose adjustment or delayed administration is beneficial to the participant's safety, the dose may be adjusted or administration may be postponed. If a dose interruption occurs, the resumption of medication can be delayed by up to 14 days to allow the participant to recover from the toxicity. If the participant has not recovered to the study-specified starting dose within 14 days, the trial will be terminated.

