4.2.2 Compliance with the criteria for starting the next treatment cycle

The study drug can be administered only after the results of the examination on the first day before the next treatment cycle confirm that all the criteria listed in the table below are met.

Table 1.1 Conforms to the criteria for starting the next treatment cycle

Hemoglobin values	$\geq 90\text{g/L}$
Neutrophil	$\geq 1.5 \times 10^9/\text{L}$

count	
platelet count	$\geq 75 \times 10^9/L$
serum total bilirubin	$\leq 1.5 \times UNL$
Aspartate transferase	$\leq 3 \times UNL$
Alanine transferase	$\leq 3 \times UNL$
Serum creatinine	$\leq 1.5 \times UNL$
diarrhoea	Compared with baseline, the number of bowel movements per day increased by less than 4 times
Oral mucositis	There was only mucosal erythema without patchy ulceration or pseudomembrane formation
Sensory nerve disorder	Feelings of abnormality or dullness that do not interfere with daily activities

Note: If an adverse reaction other than the above is found that causes a delay in the start of the next treatment cycle, the investigator will determine whether the administration of the next treatment cycle can be started when the adverse reaction is reduced or recovered.
	

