4.2.3 Study drug dose levels

If a reduction in drug dosage is required in medical practice, the dose levels of oxaliplatin and 5-fluorouracil can be adjusted according to the criteria listed in Table 1.2. Each adjustment should only reduce one dose level, and the total number of dose level adjustments throughout the study period should not exceed two. The fixed dose of suberythrocitin is 400 mg/m² or 7.5 mg/kg (for the 3-week regimen). All dose level adjustments must be clearly documented with the reasons for the adjustment.

Table 1.2 Study drug dose levels

Name of drug	Initial dose (mg/m ²)	Dose level-1 (mg/m ²)	Dose level-2 (mg/m ²)
oxaliplatin	85	65	50
5-FU	2400	2300	2200
Citrus flavonoid tablets (Aimalang)	Take orally, 500mg Tid	Take orally, 500mg twice daily	Take orally, 500mg Qd

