4.2.4 Dose adjustment criteria

Dose adjustments should be made based on the severity and duration of adverse events following the previous treatment cycle, as classified by the NCI CTCAE version 6.0. If severe hematological or liver-related adverse events occur (excluding liver function impairment due to disease progression), the doses of oxaliplatin, 5-FU, and Citrus Flavonoid Tablets (Aimalang) should be reduced simultaneously. If severe diarrhea or mucosal toxicity (excluding vomiting and hair loss) occurs, the doses of 5-FU and Citrus Flavonoid Tablets (Aimalang) should also be reduced simultaneously. See Table 1.3 for details.

Table 1.3 Dose adjustment for selected adverse events

adverse event	Severe disease classification (NCI CTCAE version 6.0)	Study dose adjustment
granulocytopenia	Grade 4 (<0.5 x 10 ⁹ /L)	Reduce the dose level
Febrile granulocytopenia	Grade 3 or above (ANC <1.0 x 10 ⁹ /L, body temperature ≥ 38.5°C)	Reduce the dose level
thrombocytopenia	Grade 3 or above (<50 x 10 ⁹ /L)	Reduce the dose level
Aspartate transferase	Grade 3 or higher (>5 x ULN)	Reduce the dose

		level
Aspartate transferase	Grade 3 or higher ($>5 \times \text{ULN}$)	Reduce the dose level
serum total bilirubin	Grade 3 or higher ($>3 \times \text{ULN}$)	Reduce the dose level

Note: If the severity of an adverse event does not meet the dose reduction criteria, but the time of administration at the beginning of the next treatment cycle is still not in accordance with the administration criteria, and it occurs repeatedly for more than 2 times, the corresponding drug should be reduced by one dose level according to the above requirements.
		

Oxaliplatin can cause characteristic neurotoxic reactions, mainly manifested as sensory nerve disorders. When the above serious adverse events occur, the oxaliplatin dose should be reduced separately, and the standard adjustment is shown in Table 1.4.

Table 1.4 Dose adjustment for cisplatin-related neurotoxicity

Adverse event	Happen	Study dose adjustment of drugs
Grade 1: abnormal or dull sensation, which can completely subside within one week	Any one of them happen	No adjustment required
Grade 2: abnormal or dull sensation, which does not completely subside during the 2 treatment cycles	Any one of them happen	Reduce the dose level
Level 3: Abnormal or dull sensation with associated dysfunction	First time happened	If the next cycle of treatment can be resumed after discontinuation,

		reduce the dose level by 1

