	The reaction failed to recover to grade 2 after discontinuation of the drug	Permanent discontinuation of medication

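### The 14-day rule in section 4.2.1 conflicts with reduced-dose resumption in Table 1.4 and does not say whether study treatment or trial participation ends

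*Combined protocol and SAP*

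**What the plan says.** Section 4.2.1 covers stopping or adjusting treatment. For mild toxicity, after consultation, "the dose may be adjusted or administration may be postponed". After a dose interruption the patient has up to 14 days to get over the toxicity before dosing resumes. The paragraph ends: "If the participant has not recovered to the study-specified starting dose within 14 days, the trial will be terminated".

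The sections that follow set out how dosing continues after toxicity:

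- **Section 4.2.2, Table 1.1** lists the conditions for starting the next cycle. For sensory nerve disorder, the most that is allowed is: "Feelings of abnormality or dullness that do not interfere with daily activities".
- **Section 4.2.3, Table 1.2** gives an initial dose and two lower levels for oxaliplatin, 5-FU and the tablets, and adds that "the total number of dose level adjustments throughout the study period should not exceed two".
- **Section 4.2.4, note to Table 1.3** concerns toxicity below the reduction threshold that still keeps the next cycle from starting on time. If "it occurs repeatedly for more than 2 times, the corresponding drug should be reduced by one dose level according to the above requirements".
- **Section 4.2.4, Table 1.4** concerns neurotoxicity, for which oxaliplatin is adjusted on its own. For a first grade 3 event: "If the next cycle of treatment can be resumed after discontinuation", then "reduce the dose level by 1". If the reaction does not return to grade 2 once the drug is stopped, the outcome is "Permanent discontinuation of medication".

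**The concern.** The closing sentence of 4.2.1 raises two problems.

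First, its condition is a return to the initial dose. A patient who is interrupted, recovers and restarts at a reduced level does not meet that condition, although Table 1.4 provides for exactly this. A site that follows 4.2.1 to the letter would stop a patient whom Table 1.4 keeps on treatment.

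Second, its consequence is that the trial is terminated, and it does not say what that means for the patient. The primary endpoint, ypTNM 0-I, is read from the surgical specimen. A patient who only stops study treatment can still go to surgery within the trial and be staged. A patient whom the site treats as withdrawn might not have the result collected.

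**Working it through.** The plan gives no figure for this rule, so the check compares its texts. The only arithmetic is the size of the dose step.

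**Step 1: the dose condition.** By Table 1.2 the oxaliplatin levels are 85, 65 and 50 mg/m². One level down is 65/85 = 76.5% of the initial dose, and two levels down is 50/85 = 58.8%.

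Take a hypothetical patient with a first grade 3 neurotoxicity. Grade 3 in Table 1.4 involves loss of function, and Table 1.1 bars a new cycle while symptoms interfere with daily activities, so dosing will normally be held. Suppose the patient recovers by day 10.

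- Table 1.4: resume oxaliplatin at 65 mg/m².
- Section 4.2.1, read literally: the patient is not back at 85 mg/m² by day 14, so the trial is terminated.

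Both instructions cannot be followed. Section 4.2.3 describes adjustments only as reductions, and nothing provides for going back up, so a patient who has been reduced has no stated route to the initial dose.

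**Step 2: how far the conflict reaches.** The sentence also fits poorly with its own paragraph, with Table 1.2 and with the note to Table 1.3, all of which foresee reduced dosing. These are tensions and not direct contradictions, because the protocol does not equate a late cycle with a dose interruption. A patient with a Table 1.3 laboratory event comes under the 14-day rule only if still outside the Table 1.1 limits when the next cycle is due. The direct conflict is the grade 3 row of Table 1.4.

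**Step 3: what ends.** The protocol has separate wording for three different events.

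- Stopping study treatment: section 4.1, for a patient given another anticancer regimen before surgery. Table 1.4 likewise stops the medication.
- Ending a patient's participation: section 4.1, as one option for a control patient who needs the tablets.
- Ending the whole study: section 14, which also speaks of terminating the trial.

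The wording in 4.2.1 is closest to section 14, which is the least plausible meaning for one patient's toxicity. The exit criteria in 3.3 do not name failure to resume within 14 days. Item (2) covers adverse events and laboratory abnormalities where continuing is not in the patient's interest, and item (8) leaves other withdrawals to the investigator. Neither says whether the 14-day rule triggers an exit.

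**Step 4: consequence for the endpoint.** Several provisions limit the damage. Section 4.1 lets a patient who cannot tolerate the planned cycles go to surgery early. Section 6.2 keeps patients who do not meet the endpoint in the denominator and continues follow-up after treatment ends or the patient withdraws. Section 8.1 analyses patients as randomised. These protect the denominator and the assignment, but they cannot supply a ypTNM stage that was not collected.

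**The case against.** The best defence is that the sentence is a translation slip. A patient recovers from a toxicity, not to a dose. The sentence just before it speaks of recovery from toxicity, and the next section lists the restart criteria. Read in sequence, the rule is that a patient who is not fit to restart within 14 days stops. The English is visibly translated elsewhere; for example, section 8.5 calls power efficiency. This stands as the likely intent and would remove the dose conflict, but the text neither refers to Table 1.1 nor says that a reduced-dose restart satisfies the rule.

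It can also be said that the paragraph opens on mild toxicity, while Table 1.4 is a specific rule for severe neurotoxicity and should prevail. This has some weight. However, the limit to mild toxicity belongs to the adjustment sentence and is not repeated for interruptions. If it did apply, mild toxicity could end the trial for a patient while grade 3 toxicity led only to a lower dose.

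On what ends, the section heading concerns treatment, Table 1.4 stops only the medication, and 4.1 allows early surgery. These favour stopping treatment, but they do not settle it.

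A reader might infer that the rule causes ypTNM to be lost, because neither the exit visit in 5.3 nor the telephone follow-up in 6.2 lists surgical pathology. The documents do not support that. None of the visit lists in section 5 names surgical pathology for any patient, including those who complete treatment, so this is a general gap in the schedule and not a result of 4.2.1.

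**Conclusion.** The point holds for the text as written. Section 4.2.1 conflicts with Table 1.4 for a patient interrupted for a first grade 3 neurotoxicity, and it does not say whether treatment or participation ends. The second ambiguity remains even if fitness to restart is what was meant. The sentence should be corrected, because it is an operative instruction that sites will apply.

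The effect on the primary comparison is expected to be small and cannot be quantified: the documents give no rate of interruption or of failure to resume. A reader might be tempted to assign the 10% dropout in section 8.5 to this rule and compute a diluted difference, but nothing links that allowance to dose interruptions. Nor do the documents show that the rule would act differently in the two arms, or that one patient's toxicity is meant to close the study.

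The issue is therefore treatment conduct and avoiding needless withdrawal before surgery. Confidence is medium, because the dose conflict rests on the literal English wording.

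**What to change.** Replace the closing sentence of 4.2.1 with:

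> If the toxicity has not recovered sufficiently to restart (Table 1.1, or the investigator's decision under its note) within 14 days, study treatment is discontinued, except that for oxaliplatin neurotoxicity Table 1.4 applies to oxaliplatin alone and the other study drugs may continue. If the criteria are met, treatment resumes at the starting dose or at the reduced level required by Tables 1.2 to 1.4. A participant who stops study treatment remains in the trial, proceeds to surgery as clinically appropriate, and has ypTNM and follow-up collected and analysed in the assigned arm.

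The neurotoxicity exception is needed. Table 1.1 includes sensory nerve disorder, so without the exception the new text would stop 5-FU and the tablets for a toxicity that section 4.2.4 handles through oxaliplatin alone.

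The cost is a wording amendment, with the sponsor review and ethics committee submission that section 13 requires. The sample size and treatment regimens do not change.
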